Herpetic events due to wild-type HSV-1 or wild-type HSV-2 which require acyclovir and are not due to talimogene laherparepvec (as confirmed by PCR testing) should not be considered as treatment related toxicity event caused by talimogene laherparepvec. Subjects may be replaced if they are not evaluable for feasibility and treatment related events (e.g., a subject did not receive both study drugs or permanently discontinued talimogene laherparepvec prior to receiving the first dose of pembrolizumab for any reason).

If dosing is delayed by more than 9 weeks from the date of the planned dose (i.e., approximately 12 weeks since the previous dose) due to the occurrence of an adverse event that is considered related to talimogene laherparepvec and/or pembrolizumab, then the subject should be taken off study treatment(s) that the adverse event is deemed to have been related to (see section 11.4.1).

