12.2 Definitions

Evaluable for toxicity – All patients will be evaluable for toxicity from the time of their first treatment with talimogene laherparepvec and/or pembrolizumab.

Evaluable for efficacy – Only those patients who have a measurable disease based on RECIST 1.1 criteria will be eligible for this study, as highlighted in Section 6.0. These patients will have their response classified according to the definitions stated below.

Only those patients who have measurable disease present at baseline, have received at least one cycle of therapy, and have had their disease re-evaluated will be considered evaluable for response. (Note: Patients who exhibit objective disease progression prior to the end of cycle 1 will also be considered evaluable. Note: one cycle of therapy consists of 21 days where the study therapy (TVEC and pembrolizumab) is administered at the start of the cycle on day 1)

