12.3.1.3 Evaluation of Best Response

The best response is the best response recorded from the start of the treatment until disease progression/recurrence (taking as reference for progressive disease the smallest measurements recorded since the treatment started). The patient's best response assignment will depend on the achievement of both measurement and confirmation criteria.

Table 13. Evaluation of Best Response – RECIST criteria

Target Lesions	Non-Target Lesions	New Lesions	Best Response	Best Response for This Category also Requires:
CR	CR	No	CR	≥ 4 wks. Confirmation
CR	Non-CR/Non-PD	No	PR	≥ 4 wks. Confirmation
PR	Non-CR/Non-PD	No	PR	
SD	Non-CR/Non-PD	No	SD	documented at least once ≥ 4 wks. from baseline
PD	Any	Yes or No	PD	no prior SD, PR or CR
Any	PD*	Yes or No	PD	
Any	Any	Yes	PD	

* In exceptional circumstances, unequivocal progression in non-target lesions may be accepted as disease progression.

Note: Patients with a global deterioration of health status requiring discontinuation of treatment without objective evidence of disease progression at that time should be reported as "***symptomatic deterioration***." Every effort should be made to document the objective progression even after discontinuation of treatment.

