12.5 Not evaluable (NE)

When no imaging/measurement is done at all at a particular time point, the patient is considered not evaluable (NE) at that time point.

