12.6 Early death

If the patient has no repeat tumor assessments following initiation of study therapy resulting from the death of the patient due to disease or treatment, it is considered early death.

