13.0 CRITERIA FOR REMOVAL FROM STUDY

Patients will be removed from the study when any of the criteria listed below applies. The reason for removal from the study and the date the patient was removed must be documented in the EDC system.

Patients may be replaced if they come off study for reasons other than progressive disease prior to receiving their second dose of talimogene laherparepvec and/or pembrolizumab. Unless otherwise stated, patients will be included in the safety and/or efficacy analyses. Patients evaluable for efficacy analysis will include all patients treated with talimogene

laherparepvec or pembrolizumab and assessable for response. Patients who are missing an assessment of response post baseline will not be considered evaluable for response unless they missed the assessment due to progression of disease in which case they will be considered non-responders for that time point. Patients who miss an assessment of response post baseline for any reason other than progression of disease will be replaced.

In the absence of treatment delays due to adverse events, treatment with intralesional talimogene laherparepvec may continue until one of the following criteria applies:

- Disappearance of injectable lesions,
- Complete response,
- Confirmed progression of disease or clinical progression,
- Intercurrent illness that prevents further administration of treatment,
- Intolerance of study treatment,
- 35 cycles from the date of the first dose of talimogene laherparepvec and Pembrolizumab in the setting of patients with locally advanced/metastatic sarcoma. Study therapy may continue beyond 35 cycles in patients who are agreeable, deemed to be clinically benefiting from study therapy and at the discretion of the investigator. Patients who discontinue study therapy after a maximum of 35 cycles of study therapy will be allowed to resume study therapy in the setting of progression of disease off study therapy.
- After completion of up to 8 cycles of study therapy in the setting of patients with operable, recurrent sarcoma who will then proceed to surgical resection of their disease
- Patient decides to withdraw from the study
- End of study, whichever occurs first.
- Physician's decision to withdraw a patient from the study for a reason not listed
- Subject is lost to follow-up

In the absence of treatment delays due to adverse events, treatment with pembrolizumab may continue until one of the following criteria applies:

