Patients evaluable for efficacy analysis will include all patients treated with talimogene laherparepvec or pembrolizumab and assessable for response. Patients who are missing an assessment of response post baseline will not be considered evaluable for response unless they missed the assessment due to progression of disease in which case they will be considered non-responders for that time point. Patients who miss an assessment of response post baseline for any reason other than progression of disease will be replaced.

Patients evaluable for safety analysis will include all patients who have received at least one dose of talimogene laherparepvec and pembrolizumab.

We expect to accrue approximately 1-2 patients each month and hence expect to finish enrollment in 10-20 months.

Additional cohorts:

Locally advanced/metastatic cohorts:

Primary End Point

The primary objective is to evaluate the efficacy of the combination therapy in each subtype-specific cohort, as assessed by the best objective response rate (complete response + partial response). The primary endpoint is best objective response rate (RECIST 1.1). It will be estimated for each subtype-specific cohort, as the proportion of evaluable patients who have complete response and partial response as defined by RECIST 1.1 criteria, with a two

sided 95% CI provided. The lower limit of the CI allowed by a sample size of 10 is provided for a range of possible ORR in the below table.

Table 15. 95% CI for estimating ORR for a Sample Size of 10 Patients

Estimated ORR	0.20	0.30	0.40	0.50
CI 95%	0.03~0.56	0.07~0.65	0.12~0.74	0.19~0.81

Patients evaluable for efficacy analysis will include all patients who have received at least one cycle of treatment with T-VEC and pembrolizumab and are assessable for response. Patients who are missing an assessment of response post baseline will not be considered evaluable for response unless they missed the assessment due to progression of disease or treatment related toxicities in which case they will be considered non-responders for that time point. Patients who miss an assessment of response post baseline for any reason other than progression of disease and treatment related toxicity will be replaced.

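### In the initial cohort, a treated patient without a post-baseline response assessment for any reason but progression leaves the ORR denominator and is replaced, and no all-treated ORR is planned

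*Combined protocol and SAP*

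**What the plan says.** For the initial 20 patients, section 14.1 limits the efficacy set to treated patients who can be assessed for response. A patient whose missed assessment is due to progression counts as a non-responder. For everyone else: "Patients who miss an assessment of response post baseline for any reason other than progression of disease will be replaced". Section 13.0 repeats this rule without naming a cohort, and adds an optional route: "Patients may be replaced if they come off study for reasons other than progressive disease prior to receiving their second dose".

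For the additional cohorts, section 14.1 is different. Patients missing an assessment are not evaluable "unless they missed the assessment due to progression of disease or treatment related toxicities in which case they will be considered non-responders". Misses for other reasons still lead to replacement.

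Four other places bear on the rule:

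- Section 12.2 says that patients with measurable disease who "have received at least one cycle of therapy, and have had their disease re-evaluated will be considered evaluable for response". It also keeps patients who progress before the end of cycle 1.
- Section 12.3.1.3: "The best response is the best response recorded from the start of the treatment until disease progression/recurrence".
- Section 12.5: where no imaging is done at a visit, "the patient is considered not evaluable (NE) at that time point".
- On a lack of repeat tumour assessments, section 12.6 says: "resulting from the death of the patient due to disease or treatment, it is considered early death". It gives no rule for counting such a patient in the ORR.

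No section defines an ORR over all treated patients.

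**The concern.** A patient who stops for toxicity, withdraws, or dies of treatment before the first scan has received the regimen and has no documented response. Under the initial-cohort rule that patient is removed from the primary denominator and someone else takes the place. Treatment failures can leave the analysis this way, and responders cannot leave by the same route. The same toxicity event is a non-response in one part of the trial and a replacement in the other, and no reason is given.

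The denominator matters most in the additional cohorts. They have no decision rule, so the ORR among about 10 evaluable patients and its confidence interval are the whole primary result. The remaining gap there is withdrawal, loss to follow-up or an unrelated event before any scan.

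The wording is also loose. To miss an assessment could mean having no post-baseline scan, or missing any single scan. On the second meaning a documented responder could be dropped.

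**Working it through.** **1. The plan's own figures.** Inputs from section 14.1: n = 20, success at 3 or more responders, null rate 5%, target rate 30%.

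- P(X ≥ 3 | 20, 0.05) = 0.0755, stated as 0.08.
- P(X ≥ 3 | 20, 0.30) = 0.9645, stated as 96%. The type II error is 0.0355, stated as 0.04.
- The exact (Clopper-Pearson) 95% CI for 3/10 is 0.067 to 0.652, given in Table 15 as 0.07 to 0.65.

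All reproduce to the precision stated.

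**2. Evaluable against all-treated ORR.** Let x be the responders, n the evaluable patients, and k the treated patients with no post-baseline scan who were replaced. The evaluable ORR is x/n. The all-treated ORR is x/(n + k), because an unscanned patient adds nothing to the numerator. The ratio is (n + k)/n, which is above 1 whenever x > 0 and k > 0. One replacement gives 21/20 = 1.05 or 11/10 = 1.10.

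Initial cohort, with x = 6 inferred from the 24-week ORR of 30% among 20 in section 4.1. The documents give no k, so the range is an assumption.

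| k | x/(20 + k) | All-treated ORR | Exact 95% CI | P(X ≥ 6) at 5% |
|---|---|---|---|---|
| 0 | 6/20 | 30.0% | 11.9 to 54.3% | 0.0003 |
| 1 | 6/21 | 28.6% | 11.3 to 52.2% | 0.0004 |
| 2 | 6/22 | 27.3% | 10.7 to 50.2% | 0.0006 |
| 3 | 6/23 | 26.1% | 10.2 to 48.4% | 0.0008 |
| 4 | 6/24 | 25.0% | 9.8 to 46.7% | 0.0010 |
| 5 | 6/25 | 24.0% | 9.4 to 45.1% | 0.0012 |

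Additional cohort, taking 3 responders among 10 evaluable as an illustration:

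| k | x/(10 + k) | All-treated ORR | Exact 95% CI |
|---|---|---|---|
| 0 | 3/10 | 30.0% | 0.067 to 0.652 |
| 1 | 3/11 | 27.3% | 0.060 to 0.610 |
| 2 | 3/12 | 25.0% | 0.055 to 0.572 |
| 3 | 3/13 | 23.1% | 0.050 to 0.538 |

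**3. Error rate of the 3-of-20 rule.** Suppose a share m of treated patients is replaced and none of them counts as a responder. An all-treated rate of 5% then corresponds to an evaluable rate of 0.05/(1 − m). P(X ≥ 3 | 20) at that rate is 0.0755 for m = 0, then 0.080, 0.085, 0.097 and 0.126 for m = 2.5%, 5%, 10% and 20%. These shares are assumptions.

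**4. The other reading.** If one missed scan is enough for exclusion, the direction can reverse. Take 7 responders among 21 treated. If one responder is dropped and the replacement does not respond, the evaluable ORR is 6/20 = 30.0% against 7/21 = 33.3% all-treated. Sections 12.2 and 12.3.1.3 fit the no-scan reading better, and section 12.5 confines non-evaluability to the visit concerned. The phrase about the time point in section 14.1 leaves it open.

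**The case against.** The evaluable set is prespecified and disclosed, and choosing it is partly a choice of estimand. The 0.08 is correct for that population. Several reasons for a missing scan are already handled: progression counts as non-response, progression before the end of cycle 1 is evaluable, early death from disease arguably counts as progression, and toxicity discontinuations enter the feasibility endpoint. The effect is also small beside the sampling error. One replacement moves 30.0% to 28.6%, against an interval about 42 points wide (54.3 − 11.9), or moves a lower limit from 0.067 to 0.060 in a cohort of 10. All of this stands and limits the weight of the point. It does not put an unscanned toxicity failure back into the initial-cohort ORR.

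A reader might infer that the reported 35% and 30% are inflated. The documents do not support that. Section 4.1 attributes them to the first 20 patients enrolled, and section 14.1 caps accrual at 20, so the plain reading is that nobody was replaced and the reported ORR already is the all-treated ORR. This cannot be confirmed, because no treated or replaced count is given and the cap does not say treated or evaluable.

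A reader might also infer that the toxicity stopping boundary limits how many patients toxicity could remove. It does not. It is defined only up to 20 patients, and it counts only attributed events that cause discontinuation or a long delay.

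**Conclusion.** The point holds as a defect in the rule, not as evidence of a biased result. Followed as written, the initial-cohort rule drops treated patients with no scan, including those lost to toxicity, withdrawal or treatment-related death. The additional cohorts close the toxicity part only.

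The size is 5% relative per replaced patient in a cohort of 20 and 10% relative in a cohort of 10. This assumes that the replaced patients had no post-baseline scan and that at least one patient responded. The initial conclusion is secure: 6 responders among 25 treated still gives P = 0.0012 against 5%. The error rates above 0.0755 rest wholly on assumed replacement shares.

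A reader might conclude that the all-treated ORR should become the primary estimate, at least in the additional cohorts. The documents do not support that either. The evaluable ORR is prespecified there, and section 16.3 in one place describes the study as completed (in another it speaks of the end of the study as still to come). Displacing a planned primary estimate once results may be known would create a worse problem. The all-treated figure belongs beside it.

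**What to change.** 1. Keep the prespecified evaluable ORR as the primary estimate in every cohort.
2. For each cohort, state how many patients were treated and how many were replaced, with reasons. If nobody was replaced in the initial cohort, one sentence settles the matter there.
3. Beside the primary estimate, report an all-treated ORR with exact 95% CI that counts every treated patient without a post-baseline assessment as a non-responder. Label it post hoc if results are already known.
4. Apply the additional-cohort toxicity rule to the initial cohort, in sections 13.0 and 14.1: a miss due to treatment-related toxicity is a non-response.
5. Reword the trigger from missing an assessment to having no post-baseline assessment, so that a documented responder who misses a later scan is kept. This agrees with sections 12.2, 12.3.1.3 and 12.5.

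The cost is a few wording changes, one added table row per cohort and a patient count. No new patients are needed. It is assumed that the data are already held. The downside is that the supplementary ORR may be slightly lower than the evaluable one.

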14.0 BIOSTATISTICS

14.1 Primary and Secondary Endpoints Statistical Considerations

The primary objective is to evaluate the efficacy, as assessed by the best objective response rate (complete response + partial response) at 24 weeks by RECIST 1.1 (primary endpoint; Phase II). The study will use a one stage design based on the exact binomial test. A 5% response rate will be considered not promising,^{94,95} a 30% response rate will be considered promising. There will be a maximum accrual of 20 patients to this study, with early stopping rules for predefined treatment-related toxicities. . It will be concluded that the true response rate is $> 5\%$ if there are 3 or more patients with an objective response among 20 patients. The design has a type I error rate of 0.08 and a type II error rate of 0.04. This design provides 96% probability of a positive result if the true response rate is at least 30%, and a 92% probability of a negative result if the true response rate is 5% or lower.

The patient population in this study represents patients with locally advanced/metastatic sarcoma that have received at least one line of previous therapy. The references supporting the 5% null rate include the PALETTE, double-blind, randomized placebo-controlled trial⁹⁴ and a study looking at the efficacy of eribulin in patients with advanced

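### Sections 14.1 and 13, read literally, remove and replace any patient who misses one response assessment, while section 12 keeps that patient and marks only the missed visit, so the primary ORR has two possible numerators and denominators.

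*Combined protocol and SAP*

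**What the plan says.** Section 14.1, original cohort: a patient lacking a post-baseline response assessment is not evaluable. If progression was the reason, the patient is a non-responder for that time point. Otherwise: "Patients who miss an assessment of response post baseline for any reason other than progression of disease will be replaced". Section 13 carries the same text. The additional-cohort paragraph of 14.1 uses the same construction and adds treatment-related toxicity to the exceptions.

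Section 12 treats the same patients differently:

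- Section 12.2: patients with measurable disease who have had at least one cycle and "have had their disease re-evaluated will be considered evaluable for response". Progression before the end of cycle 1 also counts as evaluable.
- Section 12.5: when no imaging is done at a visit, "the patient is considered not evaluable (NE) at that time point".
- Section 12.3.1.3: "The best response is the best response recorded from the start of the treatment until disease progression/recurrence".
- Section 12.4: a response needs confirmation at least 4 weeks later.

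**The concern.** The question is what happens to patients who do have post-baseline scans but miss one. Section 12 works by visit: the gap is recorded, the patient stays, and best response is read from the remaining scans. Sections 14.1 and 13 work by patient: one gap not caused by an exempt reason takes the whole patient out and brings in a replacement.

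Two analysts following different sections could therefore report different primary response rates from the same data. The trial is open and single-arm, so the choice could also be made with each patient's response already known.

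**Working it through.** **1. The two rules applied to the same patients.** Section 4.1 schedules scans at week 8 and every 8 weeks after that, so three fall by week 24 (weeks 8, 16 and 24). I read the 24-week term in the endpoint as the cut-off for best response.

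| Patient | Section 12 | Sections 14.1 and 13, literally |
|---|---|---|
| PR at week 8, confirmed at week 16, week 24 missed for a reason other than progression | Evaluable, responder | Not evaluable, replaced |
| SD at week 8, withdraws before week 16 for a non-exempt reason | Evaluable, non-responder | Not evaluable, replaced |
| Scan missed because of progression | Non-responder unless a response was already recorded | Kept, non-responder for that time point |

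The first two rows differ in both numerator and denominator. Removing the first patient lowers ORR and removing the second raises it.

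**2. The plan's own figures.** Inputs from section 14.1: "A 5% response rate will be considered not promising"; "a 30% response rate will be considered promising"; "There will be a maximum accrual of 20 patients to this study"; success is "3 or more patients with an objective response among 20 patients".

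- P(X ≥ 3 | n = 20, p = 0.05) = 0.0755. The plan states a type I error of 0.08.
- P(X ≥ 3 | n = 20, p = 0.30) = 0.9645, so the type II error is 0.0355. The plan states 0.04.

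Both reproduce. They hold only if removal from the 20 is unrelated to response.

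**3. Removal related to response (illustration).** The documents give no missed-scan rate, so the fractions here are assumptions. Suppose a fraction f of non-responders and no responders are removed and replaced. The response rate among those kept is q = p / (1 − f(1 − p)). With p = 0.05:

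| f | q | P(X ≥ 3 given n = 20, q) |
|---|---|---|
| 0 | 0.0500 | 0.075 |
| 0.10 | 0.05/0.905 = 0.0552 | 0.095 |
| 0.20 | 0.05/0.810 = 0.0617 | 0.123 |
| 0.30 | 0.05/0.715 = 0.0699 | 0.161 |

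In the other direction, suppose 20% of responders and no non-responders are removed at a true 30%. Then q = 0.24/(0.24 + 0.70) = 0.255, and power falls from 0.965 to 0.917.

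**4. Removal unrelated to response.** If responders and non-responders are removed in the same proportion, q = p. The error rate stays at 0.0755 and the power at 0.9645.

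**5. Observed data.** Section 4.1 reports 30% at 24 weeks in the first 20 patients, which is 6/20. Before any replacement, removing one responder gives 5/19 = 26.3% and removing one non-responder gives 6/19 = 31.6%. Removing three of the six responders would still leave 3.

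**6. Additional cohorts (n = 10).** One responder replaced by a non-responder moves 3/10 to 2/10. In Table 15 that is 30% (95% CI 0.07 to 0.65) against 20% (0.03 to 0.56).

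**The case against.** The strongest reply is that the conflict depends on an awkward reading. The paragraph in 14.1 opens by defining the efficacy population as treated patients who can be assessed for response, and a patient with PR on two scans plainly can be. Read with that sentence, the rule may mean patients with no post-baseline assessment, which largely agrees with 12.2. The literal reading also has no time limit, so a missed scan in year 2 would erase a responder, which the authors are unlikely to have wanted. This stands as an account of probable intent. It does not settle the text: the exception makes patients non-responders for a single time point, which is visit-level language, and nothing restricts the rule to patients with no scans.

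A reader might also infer three stronger conclusions that the documents do not support.

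- That the rule inflates ORR. Misses caused by progression are exempt, so many non-responders stay in. The removable group is largely non-progressors, which includes the responders, so the net direction is unknown.
- That the type I error is really 9.5-16.1%. That range needs selective removal of non-responders at assumed rates.
- That the 3-of-20 conclusion is in doubt. With 6/20 reported, it would take the loss of four responders, with no responder among their replacements, to fall below 3. Nothing shows that any patient was removed or replaced under this rule.

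Finally, a shift of 10 points in a cohort of 10 lies well inside the intervals in Table 15. That is true, but those intervals describe sampling error and do not cover an undefined denominator.

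**Conclusion.** The contradiction is in the current text and should be corrected. Sections 14.1 (both evaluability paragraphs) and 13, read literally, remove patients whom 12.2, 12.5 and 12.3.1.3 keep. Removal of confirmed responders follows from one reading of ambiguous wording; it is not established as practice.

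The size cannot be fixed from the documents. Under the one-directional assumption that 10-30% of non-responders and no responders are replaced, P(at least 3 of 20) at a true 5% rises from 7.5% to 9.5-16.1%. Under misses unrelated to response it does not change. The decision for the original cohort is unlikely to be affected. What is affected is the ORR estimate, most visibly in the cohorts of 10, which have no decision threshold and are judged on that estimate alone.

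**What to change.** In both evaluability paragraphs of 14.1 and in section 13:

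- limit the non-evaluable rule to patients with no post-baseline response assessment at all;
- keep every patient with at least one post-baseline assessment in the denominator, without replacement;
- treat a missed scan as not evaluable for that visit, as in 12.5, and take best response from the remaining scans.

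Narrowing the trigger alone would still allow original-cohort patients who leave before any scan because of toxicity, or who die early of a cause other than progression, to be replaced. So also state that patients with no post-baseline assessment because of progression, treatment-related toxicity or death count as non-responders, in the original cohort as well as the additional cohorts. Section 12.2 needs a matching sentence.

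The cost is a wording change with no new data, and it can be applied to data already collected. The reported ORR may shift slightly in either direction.
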